6. STATISTICAL METHODOLOGY

6.1 STATISTICAL AND ANALYTICAL ISSUES

6.1.1 Statistical Methods

All data on safety, effectiveness and exploratory endpoints will be summarized. Continuous data will be summarized using descriptive statistics including number of subjects, means, standard deviations, medians, lower and upper quartiles, and ranges. Categorical variables will be summarized with frequencies and percentages.

Effectiveness and safety data may be summarized by treatment group in previous study as described in Section 3.2 in this SAP. The effectiveness and safety data will also be summarized by age group as described in Section 6.1.3, and overall.

Point and interval estimates (95% confidence intervals) will be calculated for within treatment changes from baseline for key parameters as warranted. These within-treatment changes from baseline comparisons should be interpreted with caution, as any effect of treatment may be confounded with the time-course of disease or other factors. The primary evidence for efficacy and safety of ZX008 is based on the treatment comparisons from the double-blind studies, while the data from this OLE study provides evidence of long-term safety and effectiveness.

Confidence intervals and/or p-values, where provided for between treatment group differences, should be regarded as descriptive and not for formal inferential purposes.

All descriptive statistical analyses will be performed using SAS statistical software (Version 9.3, unless otherwise noted). Adverse events will be coded using the most recent MedDRA version available at the time of analysis. Concomitant medications will be coded using the most recent version of World Health Organization (WHO) Drug.

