6.1.2 Multiplicity Issues

This is an open-label extension study with no formal comparisons to be made between treatment groups defined by subjects' initial regimen in the previous study. Comparisons will be made within each treatment group comparing measurements observed during different time points in the OLE to the measurements obtained during the baseline period in the double-blind or PK study completed prior to this OLE.

Confidence intervals presented for descriptive purposes only will each have nominal 95% coverage probability.

No formal adjustment for multiplicity is made.

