	... Repeat for OLE Months 15, 18, 21, 24, 27, 30, 33, 36						
	OLE Last Visit	n					
		Mean (SE)					
	OLE Last VisitChg BL	n					
		Mean (SE)					

		90% CI for change from BL[5]	(xxx.x, xxx.x)	(xxx.x, xxx.x)	(xxx.x, xxx.x)	(xxx.x, xxx.x)	(xxx.x, xxx.x)	(xxx.x, xxx.x)
.....								
REPEAT FOR								
Flexibility Index (FI) (Shift + EC)[2]								
Emergent Metacognition Index (EMI) (WM + PO)[3]								
Global Executive Composite (GEC) (Inhibit + Shift + EC + WM + PO) [4]								

The BRIEF-P questionnaire was administered to preschool age children. N=# subjects in analysis population; n=number of subjects assessed at time point.
mITT = Modified Intent-to-Treat; SE=Standard Error; Chg. BL=Change from Baseline; EOS/ET=End-of-Study/Early Termination or Last available measurement.

Notes:

- [1] ISCI: Computed as the sum of the scale raw scores obtained for Inhibit and Emotional Control.
- [2] FI: Computed as the sum of the raw scale scores obtained for Shift and Emotional Control
- [3] EMI: Computed as the sum of the raw scale scores for Working Memory and Plan/Organize.
- [4] GEC: Inhibit + Shift + EC + WM + PO
- [5] Based on T distribution. Endpoints of the interval are Mean ± T*SE, where T is obtained as the 95% percentile from the Student's T distribution with n-1 degrees of freedom

Programming notes:

- 1. The rater's responses are scored as follows: 1=Never, 2=Sometimes, and 3=Often

Scales of the BRIEF-P

Scale	No. of items	Items	Scoring Instructions (for each individual)*
Inhibit	16	3, 8, 13, 18, 23, 28, 33, 38, 43, 48, 52, 54, 56, 58, 60, 62	Add up scores for items on the scale
Shift	10	5, 10, 15, 20, 25, 30, 35, 40, 45, 50	Add up scores for items on the scale
Emotional Control	10	1, 6, 11, 16, 21, 26, 31, 36, 41, 46	Add up scores for items on the scale
Working Memory	17	2, 7, 12, 17, 22, 27, 32, 37, 42, 47, 51, 53, 55, 57, 59, 61, 63	Add up scores for items on the scale
Plan/Organize	10	4, 9, 14, 19, 24, 29, 34, 39, 44, 49	Add up scores for items on the scale
Validity scales			
Inconsistency	10 pairs	(1, 11), (3, 33), (5, 45), (10, 20), (11, 26), (16, 21), (18, 52), (33, 38), (43, 52), (48, 54)	For each item in a pair, obtain the score for each item, and subtract the scores, keeping the absolute difference. Sum the 10 absolute differences to get the Inconsistency score. Classification[1]: 0-6: Acceptable 7 Acceptable ≥8: Inconsistent

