Negativity	10	30, 44, 46, 47, 53, 55, 56, 57, 59, 63	Count the number of items with a score of 3. That is the negativity score. Classification[1]: 0-2 Acceptable 3 Acceptable ≥4 Elevated

2. *Missing data handling for the BRIEF-P[2]

1. First obtain the number of missing responses for the entire questionnaire of 63 items.
2. If the total number of unanswered items is >12, do not compute any of the (five) scale raw scores (I, S, EC, WM, PO) for the BRIEF-P, as per the authors, the “protocol should be considered invalid”. In that case, all the scale raw scores will be missing, and the index scores will be missing as well.
3. If more than 2 (of the 63) items on the BRIEF-P have missing responses for a Scale (any of the 5 listed above), then a scale raw score should not be calculated. However, for any scale with 2 or fewer missing responses, impute a score of “1” for the missing item

References:

Programming Notes: Use the shell for 14.4.6.1 for the following tables.

Table 14.4.6.1.1
Behavior Rating Inventory of Executive Function-Preschool Version (BRIEF-P) – Scoring summary table
Safety Population (Japan)

Table 14.4.6.2
Behavior Rating Inventory of Executive Function- (BRIEF)
Safety Population

Table 14.4.6.2.1
Behavior Rating Inventory of Executive Function- (BRIEF)
Safety Population (Japan)

For 14.4.6.2 and 14.4.6.2.1,

Scales are:

Inhibit
Shift
Emotional Control (EC)
Initiate
Working Memory (WM)
Plan/Organize (PO)
Organization of Materials (OM)
Monitor

For Indexes Part, where we use the 90% CI for the EOS/ET measurement, the following are used, along with relevant footnotes;

Behavioral Regulation Index (BRI)[1]
Metacognition Index (MI)[2]
Global Executive Composite (GEC) [3]

For the following line, include [4] as footnote
90% CI for change from BL[4]

Footnotes

The BRIEF questionnaire was administered to school age children. N=# subjects in analysis population; n=number of subjects assessed at time point.
 mITT = Modified Intent-to-Treat; SE=Standard Error; Chg. BL=Change from Baseline; EOS/ET=End-of-Study/Early Termination or Last available measurement

Notes:

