1. If the total number of unanswered items is >14, do not compute any of the (eight) scale raw scores (INH, S, EC, INI, WM, PO, OM, m) for the BRIEF, as per the authors, the “protocol should be considered invalid”. In that case, all the scale raw scores will be missing, and the index scores will be missing as well.
2. If more than 2 (of the first 72) items have missing responses for a Scale (any of the 8 listed above), then a scale raw score should not be calculated. However, for any scale with 2 or fewer missing responses, impute a score of “1” for the missing item.
3. **IMPORTANT:** When calculating index scores, please first obtain the scale raw scores, and then the index scores are derived from the scale raw scores. Do not simply add up the scores for the individual questions.

References:

Programming Notes: Use the shell for 14.4.6.1 for the following tables.

Table 14.4.6.3
Behavior Rating Inventory of Executive Function-Adult Version (BRIEF-A) – Scoring summary table
Safety Population (De Novo Subjects)

Table 14.4.6.3.1
Behavior Rating Inventory of Executive Function-Adult Version (BRIEF-A) – Scoring summary table
Safety Population (De Novo Subjects) (Japan)

Scales are:

Inhibit
Shift
Emotional Control (EC)
Self Monitor
Initiate
Working Memory (WM)
Plan/Organize (PO)
Organization of Materials (OM)

For Indexes Part, where we use the 90% CI for the EOS/ET measurement, the following are used, along with relevant footnotes;

Behavioral Regulation Index (BRI)[1]
Metacognition Index (MI)[2]
Global Executive Composite (GEC) [3]

For the following line, include [4] as footnote
90% CI for change from BL[4]

[1] Computed as the sum of the scale raw scores obtained for Inhibit, Shift, Emotional Control, and Self Monitor.

[2] Computed as the sum of the raw scale scores obtained for Initiate, Working Memory, Plan/Organize, Organization of Materials, and Monitor.

[3] Computed as the sum of the raw scale scores for BRI and MI.

[4] Confidence interval of the mean change from baseline based on the t distribution.

Scales of the BRIEF-A

Scale	No. of items	Items	Scoring Instructions (for each individual)*

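### The BRIEF-P, BRIEF and BRIEF-A table shells specify 90% confidence intervals for change from baseline, although SAP section 6.1.2 sets 95% for descriptive intervals

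*SAP*

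**What the plan says.** Section 6.1.2 gives a general rule: "Confidence intervals presented for descriptive purposes only will each have nominal 95% coverage probability". Section 6.1.1 names the same level for this type of quantity, with a condition: "Point and interval estimates (95% confidence intervals) will be calculated for within treatment changes from baseline for key parameters as warranted".

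The BRIEF shells in Appendix 1 use another level:

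- **BRIEF-P, Table 14.4.6.1.** The index block has, under the last-visit change row, the entry "90% CI for change from BL[5". Its footnote builds the interval as mean ± T × SE, "where T is obtained as the 95% percentile from the Student's T distribution with n-1 degrees of freedom".
- **BRIEF, Table 14.4.6.2.** The programming note reads "For Indexes Part, where we use the 90% CI for the EOS/ET measurement, the following are used, along with relevant footnotes". Its footnote [4] uses the same multiplier as BRIEF-P.
- **BRIEF-A, Table 14.4.6.3.** The note again asks for "90% CI for change from BL[4". Its footnote refers to the t distribution but gives no percentile.
- **Japan copies, Tables 14.4.6.1.1, 14.4.6.2.1 and 14.4.6.3.1.** These reuse the same shells and notes.

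Section 6.4.11, the body text for BRIEF, plans mean scores, mean change to End of Study/ET and descriptive statistics. It mentions no confidence interval and no level.

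**The concern.** One document gives two levels for the same output. A programmer following the shells will produce 90% limits, while a reader relying on section 6.1.2 will expect 95%. Nothing in the SAP says which takes precedence or why BRIEF should differ.

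Section 6.4 lists BRIEF as the safety measure of cognition. No p-value is planned for it, so the interval is the only statement of uncertainty beyond the SE. Appendix 1 marks the BRIEF-P and BRIEF summary tables for the interim analysis and the 120-day safety update, and the Japan copies for the 2020 Japan report. The limits will therefore appear in several reports beside tables that use 95%.

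**Working it through.** **1. Is the 90% a slip in the label?** The shell's interval is mean ± T × SE with T = t(0.95, n-1). Its two-sided coverage is 2 × 0.95 - 1 = 0.90 at every n. The label and the formula agree. The 95 in the footnote is a one-tail percentile that leaves 5% in each tail, so it does not make the interval a 95% one. The level is also written separately for each of the three instruments. It is a consistent specification that conflicts with section 6.1.2.

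**2. What would section 6.1.2 require?** T = t(0.975, n-1), with coverage 2 × 0.975 - 1 = 0.95.

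**3. How large is the difference?** The ratio of widths is t(0.95, n-1) / t(0.975, n-1). The sizes 18, 40, 80 and 338 are approximate group totals from Table 1 of the SAP. The sizes 5 and 10 are assumptions for small cells, since each BRIEF version covers only part of the age range.

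| n | T in shell | T for 95% | shell width / 95% width | 95% width / shell width |
|---|---|---|---|---|
| 5 | 2.132 | 2.776 | 0.768 | 1.302 |
| 10 | 1.833 | 2.262 | 0.810 | 1.234 |
| 18 | 1.740 | 2.110 | 0.825 | 1.213 |
| 40 | 1.685 | 2.023 | 0.833 | 1.200 |
| 80 | 1.664 | 1.990 | 0.836 | 1.196 |
| 338 | 1.649 | 1.967 | 0.839 | 1.193 |

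For n = 18 to 338 the shell interval is 16-18% narrower than a 95% interval. At n = 10 it is 19% narrower and at n = 5 it is 23% narrower.

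**4. Non-coverage.** The two-sided figure is 10% for the shell and 5% under section 6.1.2. In one direction it is 5% against 2.5%. A simulation with n = 40, true change zero and 200,000 runs gave 9.9% and 5.0% two-sided, and 5.0% in one direction for the shell.

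**5. When would the two read differently?** At n = 40, a mean change between 1.685 and 2.023 standard errors from zero gives limits that exclude zero under the shell and include it under section 6.1.2.

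**6. What do the comparable tables do?** Section 6.3.3.5 and the shell for Table 14.2.14.2 (HADS) give a 95% t-based interval for a change from baseline, the nearest match. The intervals for seizure-frequency least squares means, responder proportions, CGI-I, palatability and status epilepticus are also 95%.

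**The case against.** The strongest reply is that nothing is miscalculated. The row says 90% and the BRIEF-P and BRIEF footnotes give the matching multiplier. The n and mean (SE) of the same change stand just above the interval, so a reader can rebuild a 95% one. Only the index rows at the last visit carry an interval; scale rows and earlier visits have none. All of this stands, and it limits the weight of the point.

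A second reply is that section 6.1.1 applies only to key parameters as warranted, and nothing names BRIEF as one. That also stands, so the clear conflict is with section 6.1.2, which has no such condition.

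A third reply is that for a safety measure a 90% interval signals possible worsening more readily. That is a legitimate reason to choose 90%, but the SAP does not give it.

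A reader might go further and infer that BRIEF changes are flagged at twice a stated error rate. The SAP does not support this. It sets no hypothesis, test, error rate or flagging rule for BRIEF, and the 10% against 5% becomes a false-signal rate only if someone treats exclusion of zero as a decision. A familywise rate across the indexes is not supported either. It would need an assumed correlation between overlapping sums of scales, and section 6.1.2 makes no multiplicity adjustment.

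**Conclusion.** The inconsistency is real and minor. Section 6.1.2 promises 95% for each descriptive interval, and the six BRIEF tables specify 90% without a stated exception. The intervals are correct as 90% intervals; they are narrow only relative to the SAP's own standard, by about 16-18% for n = 18 to 338 and by more in smaller cells. Non-coverage is 10% instead of 5%. The coverage figures assume the usual t-interval conditions, and the range of n rests on the planned group sizes, because the SAP gives no numbers per BRIEF version. No sample size, efficacy conclusion or stated decision depends on this. The document does not show which level was intended.

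**What to change.** In Tables 14.4.6.1, 14.4.6.1.1, 14.4.6.2, 14.4.6.2.1, 14.4.6.3 and 14.4.6.3.1, relabel the interval for change from baseline as 95%, and change the programming notes that mention 90% to match. In the BRIEF-P and BRIEF footnotes, define T as the 97.5th percentile of Student's t with n-1 degrees of freedom. Add the same percentile to the BRIEF-A footnote, which now has none. Name the interval and its 95% level in section 6.4.11.

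If 90% was intended, keep the shells, give the BRIEF-A footnote its percentile, and state the level with its reason as an exception in sections 6.1.2 and 6.4.11.

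The first option costs a few words and one programming constant. Its downside is intervals 19-21% wider for n = 18 to 338, so a possible worsening stands out a little less readily.

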Overall Quality of Life*		Average of 16 subscale scores*

*For each subject, an Overall Quality of Life Score will be computed by adding each subscale score for each individual and then dividing by 16.

Individual subject data for the domains will be listed.

For each subscale, descriptive statistics will be provided for the baseline, EOS/ET, and change from baseline subscale mean, overall, by treatment group and for de novo subjects.

For each treatment group at Baseline and End of Study/ET, the mean and standard deviation of the subscale score will be presented for each QOLCE subscale and for the Overall Quality of Life score.

In addition, the change from baseline in the Overall QOL score will be calculated for each subject by subtracting the baseline overall score from the overall score measured at End of Study/ET. The change from baseline for each treatment group will be summarized using the mean and standard deviation. Statistical significance of the within group change from baseline will be assessed using a Wilcoxon signed rank test.

Individual subject data for the subscales will be listed.

6.3.3.4 *Quality of Life of the Parent/Caregiver using EQ-5D-5L Scale*

The impact on the quality of life of the parent/caregiver responsible for a patient with DS will be assessed at Baseline (Core Study) and during the OLE Treatment period using the EQ-5D-5L.

The EQ-5D-5L health questionnaire is a health-related quality of life instrument with five dimensions: mobility, self-care, usual activities, pain/discomfort, and anxiety/depression. Each dimension has five possible levels: no problems, slight problems, moderate problems, severe problems and extreme problems.

The summary of results will follow the EQ-5D-5L guideline results presentation. For the “Health Profiles” descriptive system summary results will show the number, and percentage of subjects in each Item score (No Problems, Slight Problems, Moderate Problem, Severe Problem, Extreme Problems) overall and by treatment group, at baseline (Core), during the OLE treatment period and at EOS/ET. In addition, the item scores will be classified into two categories as “No Problems” and “Problems” comprised of items: slight, moderate, severe and extreme problems. Summary results will show number of patients and percentage with “No Problems” and with “Problems” overall, by treatment group and for de novo subjects, at baseline, during OLE Treatment period, and at EOS/ET.

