- [1] Computed as the sum of the scale raw scores obtained for Inhibit, Shift, and Emotional Control.
- [2] Computed as the sum of the raw scale scores obtained for Initiate, Working Memory, Plan/Organize, Organization of Materials, and Monitor.
- [3] Computed as the sum of the raw scale scores for BRI and MI.
- [4] Based on T distribution. Endpoints of the interval are Mean \pm T*SE, where T is obtained as the 95% percentile from the Student's T distribution with n-1 degrees of freedom

Programming notes:

1. The rater's responses are scored as follows: 1=Never, 2=Sometimes, and 3=Often

Scales of the BRIEF

Scale	Item	Total No. of Items for Parent Form
Inhibit	38, 41, 43, 44, 49, 54, 55, 56, 59, 65, 73, 78, 79, 81, 82	15
Shift	5, 6, 8, 12, 13, 23, 30, 39, 80, 84, 85	11
Emotional Control	1, 7, 20, 25, 26, 45, 50, 62, 64, 70	10
Initiate	3, 10, 16, 47, 48, 61, 66, 71	8
Working Memory	2, 9, 17, 19, 24, 27, 32, 33, 37, 57, 83	11
Plan/Organize	11, 15, 18, 22, 28, 35, 36, 40, 46, 51, 53, 58, 76, 77, 86	15
Organization of Materials	4, 29, 67, 68, 69, 72, 74, 75	8
Monitor	14, 21, 31, 34, 42, 52, 60, 63	8
Total No. of Items		86
Validity scales		Scoring Instructions for Validity Scales
Inconsistency	(7,25), (11, 22), (27, 17), (33, 32), (38, 59), (41, 65), (42, 63), (44, 54), (53, 60), (55, 44)	For each item in a pair, obtain the score for each item, and subtract the scores, keeping the absolute difference. Sum the 10 absolute differences to get the Inconsistency score. Classification[1]: 0-6: Acceptable 7-8: Questionable

		≥9: Inconsistent
Negativity	8, 13, 23, 30, 62, 71, 80, 83, 85	Count how many of the 9 items in the scale have a score of 3. That is the negativity score. Classification[1]: 0-4 Acceptable 5-6 Elevated ≥7 Highly Elevated

To calculate the *Behavioral Regulation Index (BRI)* raw score, sum the scale raw scores obtained for Inhibit, Shift, and Emotional Control scales.

To calculate the *Metacognition Index (MI)* raw score, sum the raw scale scores obtained for Initiate, Working Memory, Plan/Organize, Organization of Materials, and Monitor scales.

To calculate the Global Executive Composite (GEC) raw score, sum the raw scores for BRI and MI.

Missing data handling (For items 1-72 only; items 73-86 are additional clinical items)

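### The BRIEF scoring notes assign all 86 items to scales but treat items 73-86 as additional, so five scales and all three indexes have two possible scorings; the QOLCE overall score also lacks a rule for an unavailable subscale

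*SAP*

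**What the plan says.** **BRIEF (Appendix 1, notes for Tables 14.4.6.2 and 14.4.6.2.1).** The table of BRIEF scales lists item numbers for eight scales. Five rows contain items above 72:

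- Inhibit: "38, 41, 43, 44, 49, 54, 55, 56, 59, 65, 73, 78, 79, 81, 82"
- Shift: "5, 6, 8, 12, 13, 23, 30, 39, 80, 84, 85"
- Working Memory: "2, 9, 17, 19, 24, 27, 32, 33, 37, 57, 83"
- Plan/Organize: "11, 15, 18, 22, 28, 35, 36, 40, 46, 51, 53, 58, 76, 77, 86"
- Organization of Materials: "4, 29, 67, 68, 69, 72, 74, 75"

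The row "Total No. of Items" gives 86. BRI is the sum of Inhibit, Shift and Emotional Control, MI is the sum of the other five scales, and GEC is BRI plus MI. The missing-data rules follow under "Missing data handling (For items 1-72 only; items 73-86 are additional clinical items". They invalidate a scale when more than two of the first 72 items belonging to it are blank, and otherwise impute 1.

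**QOLCE (Section 6.3.3.3 and Table 10).** Items answered as not applicable (code 6) are not scored, and a subscale is the average of the subject's item responses. The Table 10 footnote says that the overall score is "computed by adding each subscale score for each individual and then dividing by 16". The recoding table under the Table 14.2.11.1 shell lists item 9.1 for reversal but not item 2.1, although Table 10 treats the two as the same subscale in different country versions.

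**The concern.** Two programmers could each follow the BRIEF notes faithfully and produce different safety tables. One would sum the rows as printed; the other would read the missing-data heading as meaning that only items 1-72 are scored. Section 6.4 names BRIEF as the measure of cognition in the safety assessment, and Table 14.4.6.2 is marked for the interim and 120-day outputs, with a Japan counterpart. Several reports therefore depend on the choice. The printed rules also leave open what happens when one of items 73-86 is blank.

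The QOLCE gap is similar but smaller. Change in the overall score is tested with a Wilcoxon signed rank test, and a subscale available at only one of the two visits could shift that change for reasons unrelated to quality of life.

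**Working it through.** **1. Reproduce the plan's own count.** Stated items per scale, in table order: 15 + 11 + 10 + 8 + 11 + 15 + 8 + 8 = 86. Counting the listed item numbers gives the same figures: 86 distinct items, covering 1 to 86, none omitted or repeated.

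**2. Remove items 73-86.** Each item scores 1 to 3, so a scale of k items ranges from k to 3k.

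| Scale or index | Items above 72 | Items as listed | Items 1-72 only | Range as listed | Range, 1-72 |
|---|---|---|---|---|---|
| Inhibit | 73, 78, 79, 81, 82 | 15 | 10 | 15-45 | 10-30 |
| Shift | 80, 84, 85 | 11 | 8 | 11-33 | 8-24 |
| Emotional Control | none | 10 | 10 | 10-30 | 10-30 |
| Initiate | none | 8 | 8 | 8-24 | 8-24 |
| Working Memory | 83 | 11 | 10 | 11-33 | 10-30 |
| Plan/Organize | 76, 77, 86 | 15 | 12 | 15-45 | 12-36 |
| Organization of Materials | 74, 75 | 8 | 6 | 8-24 | 6-18 |
| Monitor | none | 8 | 8 | 8-24 | 8-24 |
| BRI | 8 items | 36 | 28 | 36-108 | 28-84 |
| MI | 6 items | 50 | 44 | 50-150 | 44-132 |
| GEC | 14 items | 86 | 72 | 86-258 | 72-216 |

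The items left after removal number 10 + 8 + 10 + 8 + 10 + 12 + 6 + 8 = 72, exactly the number the missing-data rules use. Including the 14 adds between 14 and 42 points to GEC. The largest possible GEC change is 258 − 86 = 172 on one scoring and 216 − 72 = 144 on the other.

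**3. Missing items.** The limit of two blanks counts only items 1-72. If Inhibit is scored on 15 items, blanks in all five of 73, 78, 79, 81 and 82 would not trigger invalidation, and the rules do not say whether to impute 1 or leave those items out. For comparison, the BRIEF-P rules cover its whole 63-item form, which matches its scale table (16 + 10 + 10 + 17 + 10 = 63).

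**4. QOLCE.** Table 10 has 16 subscales, three of them single-item (Stigma, General Health, Quality of Life). If m subscales are unavailable and the others average v, a literal sum over 16 gives v × (16 − m)/16:

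- v = 50, m = 1: 50 × 15/16 = 46.9, a drop of 3.1
- v = 50, m = 4: 50 × 12/16 = 37.5, a drop of 12.5

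Dividing by the number of available subscales returns 50 in both cases. The values of v and m are illustrative; the SAP gives no frequencies.

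**The case against.** **BRIEF.** The document shows a conflict, not which side is right. The BRIEF manual is not available here, and the references under the BRIEF notes are to the BRIEF-P manual. The BRIEF scale table also lacks the explicit instruction to add up item scores that the BRIEF-P and BRIEF-A tables carry on each row. A reader might infer that the scores are wrong, or that Inhibit is inflated by 50%. Neither is established: 15/10 is a ratio of item counts, the same items would be used at every visit, and no norm or cut-off is applied to scale or index scores. What stands is that the scoring is ambiguous, and that the exact fit to 72 favours the shorter lists.

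**QOLCE.** A reader might infer that an absent subscale is scored as zero. The text does not say so; it is silent, and zero-filling would contradict Section 6.1.7.1, which rules out explicit imputation for effectiveness endpoints. A program could equally return a missing overall score. Not applicable is an item-level response, so a subscale is lost only when none of its items can be scored.

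**Item 2.1.** A reader might infer that the two QOLCE versions are scored in opposite directions. Section 6.3.3.3 requires reversal wherever needed to make 5 the best response, and that covers 2.1 whether or not it is listed. Its printed response order is not shown, so this is a point to confirm.

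**Weight.** BRIEF is summarised descriptively, and QOLCE is a secondary measure with unadjusted p-values. Changing BRIEF scoring now could also break comparability with outputs already produced. That is a reason to re-run them, not to leave the conflict in place.

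**Conclusion.** The BRIEF notes contradict themselves, and this should be resolved before the final tables. Five of eight scales and all three indexes change with the reading chosen; Emotional Control, Initiate and Monitor do not. The 72-item reading is the more likely intention, because it alone makes the missing-data rules complete. It remains an inference until the instrument's manual is checked.

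The QOLCE point is secondary. The overall score is under-specified when a subscale is unavailable. On the literal reading each absence lowers it by 1/16 (6.25%) of the mean of the available subscales; the real effect depends on a frequency the SAP does not give. The coding of item 2.1 needs confirming and is not shown to be an error.

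**What to change.** - **BRIEF.** Check the scale lists against the BRIEF manual rather than the BRIEF-P manual. Consistent with the SAP's own note, limit scale sums to items 1-72 (10, 8, 10, 8, 10, 12, 6 and 8 items in table order), correct the total to 72, and keep items 80, 83 and 85 for the Negativity count only. If the manual supports 86 items instead, extend the missing-data rules to items 73-86 and drop the description of them as additional.
- **Comparability.** Re-run any BRIEF table produced for the interim, 120-day or Japan outputs on the settled scoring.
- **QOLCE.** Define the overall score as the mean of the available subscales and state the minimum number needed; below that the score is missing.
- **Item 2.1.** Confirm from the printed form whether it needs the same reversal as 9.1, and record the answer in the recoding table.

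The cost is edits to the programming notes and the Table 10 footnote, plus the re-runs. The item responses are already listed for BRIEF, so no new data are needed.
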